## 7.2. Study Population and Setting

### 7.2.1. Inclusion criteria

- **Veterans in care without evidence of HIV infection (Obj. 1.1)- individuals will be included if they meet all of the following criteria:**

- At least one VHA health encounter in the calendar year
- $\geq 18$  years of age
- No evidence of HIV infection at the beginning of the calendar year under analysis

- **Veterans in care with a new HIV diagnosis (Obj. 1.2):**

- Incident HIV diagnosis (refer to definition in section 7.3.3)

- **Veterans in care without evidence of HIV infection who are not on PrEP but who could benefit from PrEP (Objective set 2)- individuals meeting all of the following criteria:**

- At least one VHA health encounter during the study period
- $\geq 18$  years of age
- Any of the following criteria indicating that the individual has a risk factor for HIV acquisition or a factor linked to behaviors increasing the risk of HIV acquisition and may benefit from PrEP:
  - tested for or diagnosed with a bacterial STI in the past 12 months (gonorrhea, syphilis, chlamydia),
  - tested for HIV in the past 12 months,
  - ever had alcohol use disorder,
  - ever used illicit non-injection drugs,
  - ever used injectable drugs,
  - Black women,
  - men who have sex with men,
  - individuals aged 18-24 years,
  - any history of PrEP use
- No evidence of HIV infection at the first health encounter with a criteria for PrEP

- **Veterans in care using oral PrEP only (objective set 3)**

- At least one VHA health encounter during the study period
- $\geq 18$  years of age
- Received at least one oral PrEP prescription (TDF/FTC, TAF/FTC) between January 1 2021 and 31 December 2024
- No evidence of HIV infection at the time of the first oral PrEP prescription in the study period
- Have not received a CAB LA PrEP injection between January 1, 2021, and June 30, 2025

- **Veterans in care using CAB LA for PrEP (objective set 3)**

- At least one VHA health encounter during the study period
- $\geq 18$  years of age
- Received at least one CAB LA PrEP injection between January 1, 2021 and June 30, 2025

- No evidence of HIV infection at the time of the first CAB LA PrEP injection in the study period

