### **Research Question and Objective(s)**

**Objective set 1 -Veterans in care with no evidence of HIV infection at the beginning of the calendar years under analysis**

- 1.1- Estimate the annual incidence proportion of HIV diagnoses among Veterans in care without evidence of HIV infection at the beginning of each calendar year under analysis
- 1.2- Among Veterans with an incident HIV diagnosis, characterize history of PrEP use.

**Objective set 2- Veterans in care with no evidence of HIV infection who are not on PrEP but could benefit from PrEP** (*refer to protocol section 7.2.1 for inclusion criteria*)

- 2.1- Describe the characteristics of Veterans in care who are not on PrEP but could benefit from PrEP
- 2.2- Estimate HIV testing and diagnoses rates, as well as rates of STI screening/testing rates, STI diagnoses among Veterans in care who are not on PrEP but could benefit from PrEP, over a 12-month period of follow-up

**Objective set 3- Veterans in care with no evidence of HIV infection who initiate PrEP (oral or CAB LA injectable) during the study eligibility period for PrEP initiation**

- 3.1- Describe the population of Veterans in care who initiated oral PrEP or CAB LA injectable PrEP, including their demographic and clinical characteristics, the year of PrEP initiation and the duration of follow-up
- 3.2- Describe the proportions of Veterans in care initiating CAB LA PrEP who used oral lead in (OLI) and proportion of those with direct to injection (DTI).
- 3.3- Describe adherence to oral and CAB LA injectable PrEP
  - a) Oral PrEP use only: number days oral PrEP supplied divided by number of days in the observation period
  - b) CAB LA injectable PrEP
    - Number of days covered by CAB LA PrEP divided by the number of days in the observation period
    - Timing and completion of initiation injections

- Among complete initiators with at least one maintenance injection, timing of maintenance injections: all on time, any late injection (short delay not requiring reinitiation, long delay requiring reinitiation)
  - Baseline characteristics of users with all injections on time versus users with any late maintenance injection
- 3.4- Describe patterns of PrEP use
- a) Oral PrEP:
    - Discontinuation: any discontinuation, resumption of oral PrEP
    - Duration of oral PrEP use for the first period of use
  - b) CAB LA injectable PrEP

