## **6. RESEARCH QUESTION AND OBJECTIVE(S)**

### **Objective set 1 -Veterans in care with no evidence of HIV infection at the beginning the calendar years under analysis**

- 1.1- Estimate the annual incidence proportion of HIV diagnoses among Veterans in care (actively enrolled in VHA care) without evidence of HIV infection at the beginning of

each calendar year under analysis

- 1.2- Among Veterans with an incident HIV diagnosis, characterize history of PrEP use.

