## **7. RESEARCH METHODS**

### **7.1. Study Design**

This is a cohort study using data from the Veterans Affairs National Sample, which is composed of Veterans who receive healthcare services through the Veterans Health Administration (VHA). This national sample is representative of the Veteran population, capturing a wide range of demographic, clinical, and social characteristics.

Data will be extracted from VHA's Corporate Data Warehouse (CDW), a comprehensive, regularly updated repository of information from VHA's electronic health records and administrative files. It includes patient-level data such as demographics, clinical encounters (diagnoses, interventions), laboratory and imaging results, medication details, health services utilization, and long-term health outcomes.

The study period will range from January 1, 2021, to December 31, 2025. Initiation of PrEP regimen will be assessed during the period January 1, 2021 to June 30, 2025, to allow for at least 6 months of observation following PrEP initiation.

The study will include different cohorts, as described in Table 2.

Veterans who are not on PrEP but could benefit from PrEP will be identified based on risk factors for HIV acquisition or factors linked to behaviors increasing the risk of HIV acquisition which are generally documented in Veterans health records. These risk factors include: tested for or diagnosed with a bacterial STI in the past 12 months (gonorrhea, syphilis, chlamydia) (US CDC, 2024), tested for HIV in the past 12 months, ever had alcohol use disorder (Williams, 2016), ever used illicit non-injection drugs (HIV.gov, 2024), ever used injectable drugs (CDC, 2024), Black women (CDC, 2024; Reaves, 2025), men who have sex with men (CDC, 2022; Mayer, 2021), individuals aged 18-24 years (HIV.gov, 2025 b), any history of PrEP use (Hojilla, 2021; Krakower, 2019).

---

 The US CDC recommends PrEP for people with a bacterial STI diagnosis in the past 6 months. This has been extended to testing for a bacterial STI in the past 12 months for this protocol.

**Table 2:** Description of study cohorts

Objectives	Criteria	
Objective 1a - Among all Veterans without evidence of HIV infection	Population/exposure	No evidence of HIV diagnosis at beginning of each calendar year of the study period under analysis
	Index date	N/A
	Censoring criteria	N/A
	Endpoint	HIV diagnosis

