### 7.3.3. Outcome definitions

#### ◆ Veterans without HIV (Objective 1)

Incident HIV diagnosis: a new HIV diagnosis is defined as either having a (1) positive screening antibody test with positive confirmatory antibody testing, (2) positive HIV viral load, or (3) documentation of HIV on the EHR problem list.

All potential HIV incident diagnosis will be subject to a detailed review for confirmation.

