### 7.7.1. Primary analysis

#### 7.7.1.1. Main Analytical approach

##### **Veterans in care without HIV (Objective 1.1)**

For each calendar year during the study period, the number and percentage of new HIV diagnoses will be reported out of all individuals receiving care in the VHA healthcare system.

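### Objective 1.1 fixes HIV-free status on 1 January but not membership in VHA care, so pre-existing HIV in Veterans first seen mid-year can be counted as a new diagnosis

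*Protocol*

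**What the plan says.** Protocol section 6 sets the target: "Estimate the annual incidence proportion of HIV diagnoses among Veterans in care (actively enrolled in VHA care) without evidence of HIV infection" at the start of each calendar year. It does not say on what date a Veteran must be enrolled.

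Section 7.2.1 gives three conditions for Objective 1.1: age 18 or over, "At least one VHA health encounter in the calendar year", and "No evidence of HIV infection at the beginning of the calendar year under analysis". It asks for no earlier encounter, look-back period or previous negative test. Table 2 repeats the HIV-free condition ("No evidence of HIV diagnosis at beginning of each calendar year of the study period under analysis") and marks index date and censoring as not applicable.

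Section 7.3.3 accepts any one of three routes to a new diagnosis: a confirmed positive antibody screen, a positive viral load, or HIV on the problem list. It adds: "All potential HIV incident diagnosis will be subject to a detailed review for confirmation".

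Section 7.7.1.1 reports new diagnoses "out of all individuals receiving care in the VHA healthcare system", although the heading over that sentence limits the group to Veterans without HIV.

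Objective 1.2 takes its cases from the same definition. It classifies them by PrEP history: never, within 12 months before diagnosis, or earlier.

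**The concern.** An incidence proportion needs a group that is under observation and free of the event when the risk period opens. Here the HIV-free condition refers to 1 January, but the in-care condition can be met on any later day of the year. Someone with no VHA record on 1 January has no VHA evidence of HIV on that date, whatever their true status.

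Two of the three case routes can be met by long-standing HIV. A detectable viral load does not date the infection, and a problem-list entry can simply record a diagnosis made elsewhere. Nothing in the definition refers to when HIV was first diagnosed.

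Two results are at stake. The annual incidence proportion can be too high. In Objective 1.2, a new entrant has little or no VHA PrEP record, so a misclassified case would tend to fall in the never-used-PrEP group. That would distort a central description in a study of PrEP use.

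**Working it through.** **1. Following one Veteran through the rules.** Suppose HIV was diagnosed outside VHA in an earlier year and the first VHA visit is in June.

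- In care during the year: met by the June visit.
- No HIV evidence at the start of the year: met, because there is no VHA record before June.
- New diagnosis: met through the problem list, or through a detectable viral load.
- Confirmation review: the person does have HIV, and no written rule tells the reviewer to reject HIV that predates VHA entry.
- Objective 1.2: its only inclusion criterion is an incident diagnosis, so the case carries over.

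**2. Size before review.** The Protocol gives no expected incidence, event count or precision for Objective 1.1, so there is no figure to reproduce. Inputs:

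- N = 6,000,000 accessing care per year (Protocol section 7.4, approximate).
- e, share of these new to VHA in the year: assumed 2% to 8%.
- p, share of entrants with pre-existing HIV first recorded in VHA that year: assumed 0.05% to 0.5%.
- i, true incidence of new diagnosis: assumed 5 to 20 per 100,000.

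True cases = N × i. Added cases = N × e × p. Ratio of reported to true = 1 + e × p / i.

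| Scenario | e | p | i per 100,000 | True cases | Added cases | Reported per 100,000 | Ratio |
|---|---|---|---|---|---|---|---|
| Lowest ratio | 2% | 0.05% | 20 | 1,200 | 60 | 21 | 1.05 |
| Middle | 5% | 0.1% | 10 | 600 | 300 | 15 | 1.5 |
| Highest ratio | 8% | 0.5% | 5 | 300 | 2,400 | 45 | 9.0 |

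In the middle scenario, 300 of 900 cases (one third) passed to Objective 1.2 would be pre-existing HIV.

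**3. Effect of the review.** If the review removes a fraction r of the added cases, the ratio is 1 + (1 − r) × e × p / i. In the middle scenario with r = 0.5 it is 1 + 0.5 × 0.5 = 1.25. With r = 1 the bias disappears. The Protocol gives no basis for choosing r.

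**4. Denominator wording.** Dividing by everyone in care instead of those without HIV multiplies the proportion by 1 − (HIV prevalence among all in care). At an assumed prevalence of 0.1% to 1%, a true 10 per 100,000 becomes 9.99 to 9.90. This is at most 1%, and downward.

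**The case against.** The strongest reply is that section 7.3.3 sends every potential incident case to a detailed review. What is reviewed is a potential incident diagnosis, not merely HIV status, and the laboratory and medication data could help a reviewer recognise established infection. Detailed adjudication rules may sit in an analysis plan that is not shown. This stands in part: the review may remove some or all such cases. It does not close the gap. The Protocol itself fixes the inclusion criteria and the case definition, and neither mentions HIV that predates VHA entry. The described data source is VHA's own records, so outside diagnosis dates may be missing. Section 10 also places the study in a class that works from structured data, or from unstructured data without human review, which makes it unclear how far clinical notes would be read.

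A reader might infer three stronger things that the Protocol does not support:

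- That transferred-in HIV is certain to be counted as incident, or that the count is roughly doubled. Every input except N is assumed, the calculation is before review, and the low end is a 5% excess.
- That the at-risk set has no anchor at all. HIV-free status is fixed at the start of the year in the synopsis, section 6, Table 2 and section 7.2.1; only care membership floats.
- That the section 7.7.1.1 denominator is a material error. It is a wording conflict under a heading that already says without HIV, with a negligible effect.

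It is also fair to say that requiring an encounter in the year is useful. Without it the denominator would include Veterans who never attend and could not be diagnosed in VHA that year.

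**Conclusion.** The point holds as a gap in the definitions. Under the rules as written, HIV already present in a Veteran first seen during the year can enter the Objective 1.1 numerator and carry into Objective 1.2. The direction of any resulting bias is upward for incidence and towards never-used-PrEP in the PrEP history.

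The size is not known. Before review, the assumed ranges give a ratio of 1.05 to 9. This supposes that every entrant counted in p meets the definition and that none is removed. The bias after review cannot be estimated from the Protocol. The change should be made because it is cheap and the possible bias is not small, not because a particular inflation has been shown.

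**What to change.** 1. In section 7.2.1, keep the in-year encounter and add at least one VHA encounter before 1 January, for example within the preceding 24 months. Use the same set for numerator and denominator of the main estimate. The 24 months is one workable choice and is not derived from the Protocol. A look-back is available even for 2021, because section 7.4 describes a sample reaching back to 2000.
2. Report diagnoses in Veterans first seen during the year in a separate row, labelled as newly recorded in VHA with timing unknown. Say also where Veterans returning after a gap longer than the look-back are counted. Apply the same split to Objective 1.2.
3. In section 7.3.3, state that the review excludes HIV documented or treated before the recorded diagnosis date. This is needed even with the look-back, because an established VHA patient can also be diagnosed elsewhere.
4. Add a sensitivity analysis limited to Veterans with a prior negative HIV test.
5. As a minor correction, change the section 7.7.1.1 denominator to adults in care without HIV evidence, to match 7.2.1.

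The cost is Protocol wording, one look-back query and an extra table row. The real downside is that genuine new diagnoses among new entrants leave the main estimate and appear only in the separate row, so the headline figure describes Veterans already in VHA care.

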have not consistently used a condom, or have been diagnosed with a sexually transmitted infection (STI) in the past six months (US CDC, 2024). PrEP is also recommended to people who inject drugs and have an injection partner with HIV, or share needles, syringes, or other equipment to inject drugs. People who have been prescribed PEP (post-exposure prophylaxis) and report continued risk behavior or have used multiple courses of PEP may as well consider taking PrEP. People may also choose to take PrEP, even if these behaviors do not apply to them.

In 2022, of approximately 1.2 million people in the US who could benefit from PrEP, it was estimated that only around 36% had received a PrEP prescription (Fanfair, 2023). The Department of Veterans Affairs (VA) is the largest HIV care provider in the US; PrEP is a covered benefit for all enrolled Veterans (Huang, 2018). An analysis of 2014-2022 data of the Veterans Health Administration (VHA) showed an increase in the number of Veterans prescribed PrEP annually, from 361 in 2014 (5.6 per 100,000 Veterans in VHA care) to 6050 in 2022 (89.4 per 100,000) (Huang, 2025). While adherence to oral PrEP was high among Veterans in the period 2012-2016 (Huang, 2018), recent adherence data, including for long-acting injectable PrEP, are lacking. To be eligible for CAB-LA PrEP in the Veterans Health Administration, individuals must be at substantial risk of HIV acquisition (sex without condoms, recent or frequent sexually transmitted infections, sexual relationship with HIV infected partner, injection drug abuse with equipment sharing), prescribed cabotegravir by a provider experienced in PrEP, and meet at least one of the following additional criteria: intolerance to TDF/FTC or TAF/FTC, renal dysfunction, challenges with adherence to daily oral PrEP, or very high risk of HIV acquisition. Patients are excluded if they have significant noncompliance with follow-up or drug interactions with CAB (VA, 2022).

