## 7.5. Study size

This study is not designed for hypothesis testing but aims to evaluate usage patterns of oral PrEP and CAB LA PrEP in clinical practice. Additionally, it seeks to describe the incidence of HIV diagnoses among Veterans in care, including their PrEP history, as well as the incidence of HIV and other STI diagnoses among Veterans not on PrEP but potentially eligible for it. The study focuses on multiple outcomes of interest, with several parameters to be estimated.

For the objective related to HIV incidence among Veterans, the study will leverage data from the entire eligible population of Veterans in care.

Regarding PrEP usage patterns, a feasibility assessment identified 15,477 oral PrEP users and 748 CAB LA PrEP users between January 1, 2021 and June 30, 2025.

Table 4 provides precision estimates for proportions using a 95% confidence level, calculated using the standard confidence intervals equation  $[p \pm 1.96\sqrt{(p*(1-p)/N)}]$ . In the oral PrEP group, confidence interval widths for evaluated proportions range from 0.01 to 0.02. For the CAB LA PrEP group, the confidence interval width ranges from 0.04 to 0.07.

For instance, if the proportion of individuals having a complete CAB LA PrEP initiation is 80%, the 95% confidence interval around this estimate will be 77-83%.

**Table 4:** Precision estimates based on sample size and event proportions, using a 95% confidence level

PrEP formulation	Sample Size	Event Proportion	Lower Limit	Upper Limit	CI Width
CAB LA	748	0.1	0.08	0.12	0.04
	748	0.2	0.17	0.23	0.06
	748	0.3	0.27	0.33	0.07
	748	0.4	0.36	0.43	0.07
	748	0.5	0.46	0.54	0.07
	748	0.6	0.57	0.64	0.07
	748	0.7	0.67	0.73	0.07
	748	0.8	0.77	0.83	0.06
	748	0.9	0.88	0.92	0.04
Oral PrEP	15477	0.1	0.10	0.10	0.01
	15477	0.2	0.19	0.21	0.01
	15477	0.3	0.29	0.31	0.01
	15477	0.4	0.39	0.41	0.02
	15477	0.5	0.49	0.51	0.02
	15477	0.6	0.59	0.61	0.02
	15477	0.7	0.69	0.71	0.01
	15477	0.8	0.79	0.81	0.01
	15477	0.9	0.90	0.90	0.01

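### Oral PrEP entry closes on two different dates, the oral-only cohort is selected on later CAB LA use, and Table 4's CAB LA widths do not fit the maintenance-based endpoints

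*Protocol*

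**What the plan says.** **Entry window.** Protocol section 7.1 sets one window without distinguishing regimens: "Initiation of PrEP regimen will be assessed during the period January 1, 2021 to June 30, 2025". The reason given is "to allow for at least 6 months of observation following PrEP initiation", and on the study end it states: "The study period will range from January 1, 2021, to December 31, 2025". Section 7.5 uses the same window: "a feasibility assessment identified 15,477 oral PrEP users and 748 CAB LA PrEP users between January 1, 2021 and June 30, 2025". Section 7.2.1 keeps 30 June 2025 for CAB LA but requires of the oral cohort: "Received at least one oral PrEP prescription (TDF/FTC, TAF/FTC) between January 1 2021 and 31 December 2024". It gives no reason for the earlier date.

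**Later CAB LA use.** The oral cohort is titled as oral PrEP only and carries the criterion "Have not received a CAB LA PrEP injection between January 1, 2021, and June 30, 2025". Table 2 sets the objective set 3 index date at the first PrEP regimen in the study period. Its censoring list for days covered has death, loss to follow-up, study end and 12 months, but no switch. Section 5 lists the additional VHA criteria for CAB LA, of which at least one must be met: intolerance to oral PrEP, renal dysfunction, "challenges with adherence to daily oral PrEP", or very high HIV risk.

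**Precision.** Section 7.5 states: "For the CAB LA PrEP group, the confidence interval width ranges from 0.04 to 0.07". All CAB LA rows of Table 4 use N=748. Section 7.3.3 restricts maintenance timing, and all CAB LA outcomes under objective 3.4, to complete initiators with at least one maintenance injection.

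**The concern.** Three things do not fit together.

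1. A programmer cannot satisfy sections 7.1, 7.2.1 and 7.5 at once. Oral starters of January to June 2025 are inside the design window and the feasibility count but outside the inclusion criteria.

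2. Whether a Veteran belongs to the oral cohort cannot be known at the index date. Someone who starts oral PrEP in 2021 and receives CAB LA in 2023 has oral PrEP as first regimen under Table 2, yet is barred from the oral cohort. Objectives 3.1, 3.4a and 3.5 are worded for oral initiators or by modality. The Veterans removed are unlikely to be a random subset, because two of the section 5 criteria concern oral adherence and HIV risk, which bear directly on the outcomes.

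3. The stated CAB LA precision is that of all 748 users, while several of the main CAB LA proportions have a smaller denominator.

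**Working it through.** **Windows side by side.** Oral entry is 48 months in 7.2.1 and 54 months in 7.1 and 7.5; CAB LA entry is 54 months throughout. Minimum potential follow-up to 31 December 2025 is 365 days from 31 December 2024 and 184 days from 30 June 2025.

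**Reproducing Table 4.** Width = 2 × 1.96 × √(p(1−p)/N).
- Oral, N=15,477: 0.0095 at p=0.1 and 0.0158 at p=0.5. All rows agree after rounding.
- CAB LA, N=748: 0.0430 at p=0.1 and 0.0717 at p=0.5. All widths agree. Two limits (upper at 0.4, lower at 0.6) agree once p is taken as a whole count: 299/748 gives 0.4348 and 449/748 gives 0.5652.

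Table 4 has no arithmetic error.

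**Oral precision under the shorter window.** The protocol gives no oral count to 31 December 2024, so N is assumed.
- Uniform accrual: 15,477 × 48/54 = 13,757 (1,720 fewer); widest interval 2 × 1.96 × √(0.25/13,757) = 0.0167.
- Also removing all 748 CAB LA users: N = 13,009; widest 0.0172.
- N = 10,000: widest 0.0196.

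All still round to the stated maximum of 0.02.

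**Bound on the selection effect.** Let N be the oral users kept, k the oral starters removed for later CAB LA, p the proportion among those kept and q among those removed. Restoring the removed changes the proportion by k(q−p)/(N+k). The extremes are q=1 and q=0. N = 15,477 assumes that this count already excludes CAB LA users, which section 7.5 does not say. The number k is not given; it is at most 748.
- k=748, p=0.1: 748 × 0.9/16,225 = +0.0415 (q=1); 748 × 0.1/16,225 = −0.0046 (q=0).
- k=748, p=0.5: 748 × 0.5/16,225 = ±0.0231.
- k=100, p=0.1: 100 × 0.9/15,577 = +0.0058 (q=1). At p=0.5: ±0.0032.
- With N=13,757, k=748, p=0.1: 748 × 0.9/14,505 = +0.0464.

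The 95% half-widths at N=15,477 are 0.0047 (p=0.1) and 0.0079 (p=0.5).

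For the oral HIV rate, switchers who are HIV-free at the switch leave with their oral person-time, while those diagnosed on oral PrEP stay. If switchers had average person-time, the rate rises by at most 748/15,477 = 4.8%.

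**Switches after 30 June 2025.** The exclusion stops at that date and Table 2 does not censor at a switch. An oral user who moves to CAB LA in July to December 2025 therefore stays in the oral cohort. Under the refill-gap rule of section 7.3.3 the move can count as oral discontinuation. If the 12 months after index are still running, the remaining days stay in the coverage denominator.

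**CAB LA denominators.** The share reaching a maintenance injection is not given; 60-80% is an assumption.
- 80%: 0.8 × 748 = 598; widest 2 × 1.96 × √(0.25/598) = 0.080.
- 60%: 0.6 × 748 = 449; widest 2 × 1.96 × √(0.25/449) = 0.092.

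The stated maximum is 0.07.

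**The case against.** **The cohort is openly labelled.** It is called oral only, objective 3.3a is worded for oral use only, the study is descriptive, and its only tests compare subgroups within CAB LA users. This stands in part: for a group so defined, the exclusion defines the population. It does not help where results are read as those of oral initiators or by modality (3.1, 3.4a, 3.5).

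**The earlier date may be deliberate.** It would give every oral user 12 months of potential follow-up. The protocol does not say so, and CAB LA has the same 12-month coverage endpoint without that cut-off. Nor is such a restriction required, since coverage is already censored at study end and divided by observed days.

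**Stronger readings the documents do not support.** A reader might infer that the date conflict itself biases the oral results. It does not; it changes cohort size and follow-up. Even the loss of 1,720 users is uncertain: 7.2.1 admits anyone with a prescription in the window, so continuing users enter early and the loss may be smaller.

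A reader might also infer that oral adherence is shown to be flattered. It is not. Two of the four additional criteria, intolerance and renal dysfunction, are not adherence problems, and section 5 also excludes patients with significant noncompliance with follow-up, which may pull the other way. The number of switchers and their adherence are not given. Coverage is summarised by median and interquartile range, so a shift in mean adherence cannot be set against Table 4's half-widths for binary proportions.

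Nor does Table 4 fail for CAB LA generally. Its worked example, complete initiation, rightly uses all users with an injection, and oral lead-in, days covered and objective 3.5 are not limited to maintenance users. Finally, counting a late switch as stopping oral PrEP is literally correct; what is lost is the distinction between switching and stopping PrEP.

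**Conclusion.** The point holds in three limited parts.

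- **Dates:** a plain contradiction. It must be resolved before the cohort is built, but its effect on oral precision is negligible (widest interval 0.0158 to about 0.017 under uniform accrual).
- **Selection:** the oral cohort is conditioned on a post-index event that is plausibly related to the outcomes. Bias in results read as those of oral initiators is possible, and its direction is not established. The worst-case bound is 4 to 5 points on a 10% proportion and 2.3 points on a 50% proportion at N=15,477. With 100 switchers it is 0.6 and 0.3 points. These are bounds under stated assumptions, not estimates. Switches after 30 June 2025 are handled differently from earlier ones.
- **CAB LA precision:** Table 4 is correctly calculated but does not describe the maintenance-timing, discontinuation and persistence proportions. If 60-80% of the 748 qualify, the widest interval is about 0.08-0.09 instead of 0.07, a modest loss in a study without hypothesis testing.

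**What to change.** 1. State one oral entry window in sections 7.1, 7.2.1 and 7.5, with the reason if it differs from that for CAB LA. Restate the oral N for that window, and say whether it excludes CAB LA users.
2. Keep all oral initiators from their index date. In the analysis, censor oral follow-up at the first CAB LA or LEN injection, at whatever date up to study end, and report switching as its own outcome. If an oral-only group is kept, label it as such wherever it is reported and show the all-initiator result beside it.
3. Add CAB LA rows to Table 4 for complete initiators with at least one maintenance injection, using the actual count or a stated range such as 449 to 598.

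**Cost:** protocol wording and a feasibility recount; no new data collection. Some Veterans will contribute to both modalities at different times, so the two groups are no longer mutually exclusive, and the stated CAB LA precision becomes less favourable.
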